AIMS (1) Determine the anxiety levels of women with suspected endometrial cancer
(2) Determine factors affecting anxiety levels

OUTCOME MEASURES Primary outcome measures:
(1) Anxiety levels of women with suspected cancer

Secondary outcome measures:
(1) Factors affecting anxiety level

POPULATION 250 women referred to rapid access clinic with postmenopausal bleeding or intermenstrual bleeding.

ELIGIBILITY All women presenting to rapid access gynaecology clinic with postmenopausal bleeding or intermenstrual bleeding

EXCLUSION Anyone lacking capacity. <18years old. Pregnant. Any contra-indication carry out a biopsy

DURATION 1 year

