3. STUDY DESIGN

Paired observational study

Setting: Imperial College NHS Trust Hospitals, London

Participants: 250 women referred to rapid access clinic with postmenopausal bleeding or intermenstrual bleeding.

Duration: 1 year

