3.1 MAIN STUDY

250 consecutive women presenting to the rapid access clinic with postmenopausal bleeding (PMB) and intermenstrual bleeding (IMB) will be approached for consent for inclusion into this study.

Women were given a short 5-minute questionnaire to fill during their first clinic attendance, before seeing any clinician or healthcare provider (see appendix for copy of questionnaire).

The questionnaire had 19 questions, split into 4 broad groups: questions quantifying anxiety/stress levels, factors that might affect anxiety levels, patient's perception of cancer diagnosis and the importance of a quick diagnosis. Patients were asked to score how they perceived their stress levels using a Likert scale. A score of 4 or above was defined as high stress in this study and 3 and below as low stress. Patients were also asked to fill a Generalised Anxiety Disorder 7 (GAD 7) form.

Women were excluded if, in the absence of a translator, they did not have sufficient comprehension of English to fill the questionnaire. Patients were also excluded from the analysis if they omitted 3 or more answers from the questionnaire.

For women needing a pipelle biopsy for clinical indications, the time taken to perform the biopsy, from insertion of the speculum to its removal was recorded in minutes, rounded to the nearest 30 seconds. Women were asked to rank their pain using a visual analogue score (0 to 10, where 0 is no pain and 10 is the worst pain in their life). Women were asked if they would have this procedure again, if they would recommend it to family or friends should they were need it. If women persisted with the procedure, they were asked their motivations for doing so, and what coping mechanisms they used. This paired data was matched to the patient's questionnaire responses.

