7. STATISTICS AND DATA ANALYSIS

Microsoft excel was used to provide the graphs and pie charts for demographics. SPSS version 25 was used to perform all the sub analyses. Median, quartile ranges, box and whiskers plots were created for each variable. A Mann-Whitney-Wilcoxon test was used to assess for association between each factor and anxiety as measured with GAD 7 score.

Data and all appropriate documentation will be stored for a minimum of 10 years after the completion of the study, including the follow-up period.

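### Does naming only a two-group rank test leave the anxiety factors and the matched biopsy data without a usable analysis?

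*Combined protocol and SAP*

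**What the plan says.** The synopsis lists the anxiety level as the primary outcome and "Factors affecting anxiety level" as the only secondary outcome. Section 2 repeats these as the two objectives.

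Section 3.1 describes a 19-item questionnaire in four groups. One group measures anxiety and stress; a separate group covers "factors that might affect anxiety levels". The questionnaire is completed "before seeing any clinician or healthcare provider". The Likert stress score has the only cut-off in the document: "A score of 4 or above was defined as high stress in this study and 3 and below as low stress". Women also complete the GAD-7.

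For women who need a biopsy, section 3.1 adds procedure time, a 0 to 10 pain score, willingness to repeat or recommend the procedure, motivations and coping mechanisms. On linkage it says: "This paired data was matched to" the same woman's questionnaire answers. Section 3 labels the design "Paired observational study".

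Section 7 is the whole analysis plan. It gives medians, quartiles and box plots for every variable, and one inferential sentence: "A Mann-Whitney-Wilcoxon test was used to assess for association between each factor and anxiety as measured with GAD 7 score".

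**The concern.** Mann-Whitney-Wilcoxon compares two independent groups. If a factor has three or more ordered or unordered levels, or is continuous, the named test can be used only after the factor is cut in two or its levels are compared pair by pair. The plan gives no rule for either, so the cut or the set of pairs could be chosen once the data are seen. A cut also discards information, and uncorrected pairwise tests raise the chance of a false positive. This would bear on the only secondary outcome.

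The biopsy data seem to have a similar gap. Pain and procedure time take many values and have no cut-off. They are matched to the questionnaire, and the design label refers to the pairing, yet no test or direction is given for the link. Several analyses would be possible after the results are known.

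**Working it through.** The plan has no figure to reproduce: it states no alpha, power, effect size or number biopsied. The check is therefore which variables the test sentence governs, and then what a poor choice would cost.

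**Step 1. Variables and scales (section 3.1) against the named test.**

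| Variable | Scale visible in the text | Listed aim or outcome? | Does a two-group test against GAD-7 fit? |
|---|---|---|---|
| Items in the factors group | None; the questionnaire is not in the text available | Yes, secondary | Yes if two-level; otherwise only after a cut |
| Likert stress score | Likert, cut at 4 | Grouped with the anxiety and stress measures | Not a factor on the natural reading; if used for grouping, its cut is already fixed |
| Biopsy pain | 0 to 10 | No | Not without a cut |
| Biopsy time | Nearest 30 seconds | No | Not without a cut |
| Willingness to repeat or recommend | Not stated; reads as yes/no | No | Yes if yes/no |

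The only row that feeds the secondary outcome is the first, and its number of levels cannot be seen. Naming a two-group test for each factor is consistent with two-level items.

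**Step 2. Timing.** The questionnaire comes before any clinician contact, and the GAD-7 is described with it, although the GAD-7 sentence gives no separate time. On that reading anxiety precedes the biopsy. Pain and procedure time then cannot be factors that affect it, so the test sentence does not govern them. What section 7 states for them is the descriptive summary. Paired here means two records from one woman, not one measure taken twice, so no signed-rank or other paired test is missing.

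**Step 3. Hypothetical cost of cutting a continuous factor.** For a normal factor split with upper share p, the share of information kept is φ(q)² / [p(1 − p)], where φ is the standard normal density and q the cut point:

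- p = 0.5: 0.3989² / 0.25 = 0.637
- p = 0.3: 0.3477² / 0.21 = 0.576
- p = 0.2: 0.2800² / 0.16 = 0.490

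Simulated power, with assumed two-sided alpha 0.05, a normal factor and a skewed 0 to 21 anxiety score:

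| Women analysed | Correlation | Spearman, uncut | Mann-Whitney, median split |
|---|---|---|---|
| 250 | 0.10 | 0.32 | 0.24 |
| 250 | 0.15 | 0.62 | 0.44 |
| 250 | 0.20 | 0.86 | 0.69 |
| 250 | 0.30 | 1.00 | 0.97 |
| 200 | 0.20 | 0.77 | 0.58 |

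The 200 row is there because 250 is the number of women who "will be approached for consent for inclusion into this study", not the number analysed. With no true association, both tests rejected about 5% of the time (0.048 and 0.051). The cut therefore costs power and does not invalidate the test.

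For pain against GAD-7, with 100 to 250 women biopsied and correlations of 0.20 to 0.30 (all assumed), a median split lost between 4 points (1.00 against 0.96) and 18 points (0.82 against 0.64).

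**Step 4. Hypothetical cost of testing all pairs of levels.** With 3, 4 and 5 levels there are 3, 6 and 10 pairs. If the tests were independent, the chance of at least one false positive would be 1 − 0.95³ = 0.143, 1 − 0.95⁶ = 0.265 and 1 − 0.95¹⁰ = 0.401. Pairs share groups, and simulation with 250 women gives 0.13, 0.19 and 0.28. A single Kruskal-Wallis test gave 0.055, 0.047 and 0.041.

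Steps 3 and 4 cost practices that the plan does not prescribe: it contains no median split and no all-pairs testing. For a two-level factor both costs are zero.

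**The case for a change.** The best case for a change is that one of the two objectives rests on a single sentence, and that sentence is complete only if every factor has two levels. The biopsy half does not depend on the unseen questionnaire: section 3.1 gives the scales for pain and time, the design label refers to the pairing, and no analysis of the link is stated. A few sentences in section 7 would close both gaps with the same data and software, and would remove the freedom to choose a cut after seeing results.

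Part of this stands. Section 7 gives no rule for factors with more than two levels and no inferential analysis of the matched data.

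The rest is weaker. The first gap depends on factors that cannot be shown to exist. The stress score does not fill that hole: section 3.1 places it with the measures of anxiety and stress, apart from the factors, and its cut is stated in advance. The second gap concerns variables outside the aims and outcomes, where any link to GAD-7 would be exploratory whatever was written. Parts of sections 3.1 and 7 are in the past tense, so data may already have been collected; text added now might count only as post hoc and would not restore prespecification.

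**Conclusion.** No change is called for. The plan leaves a method unwritten for cases that may not arise, and no rule it does state is shown to give a wrong result. For two-level factors the named test is suitable and the loss is nil. If a factor with more levels turns up, the ordinary choices are Kruskal-Wallis for unordered levels and a rank correlation for ordered or continuous ones, and a competent analyst would make them unprompted. Pain and biopsy time already have descriptive summaries, which is enough for data that serve no listed outcome.

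The power differences, up to about 19 points in the cases shown (0.77 against 0.58), rest entirely on assumed alpha, correlations, distributions and numbers analysed, and on a split the plan does not propose. They show what a poor choice could cost, not a flaw in this plan. The conclusion rests on two readings: that the stress score is a measure and not a factor, and that GAD-7 is completed with the questionnaire before the biopsy. It would need another look if the questionnaire showed several many-level factors that had in fact been cut without a stated rule. The primary outcome is untouched either way.

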8. REGULATORY ISSUES

8.1 ETHICS APPROVAL

The Chief Investigator has obtained approval from the Research Ethics Committee. The study must be submitted for Site Specific Assessment (SSA) at each participating NHS Trust. The Chief Investigator will require a copy of the Trust R&D approval letter before accepting participants into the study. The study will be conducted in accordance with the recommendations for physicians involved in research on human subjects adopted by the 18th World Medical Assembly, Helsinki 1964 and later revisions.

8.2 CONSENT

Consent to enter the study must be sought from each participant only after a full explanation has been given, an information leaflet offered and time allowed for consideration. Signed participant consent should be obtained. The right of the participant to refuse to participate without giving reasons must be respected. After the participant has entered the study the clinician remains free to give alternative treatment to that specified in the protocol at any stage

if he/she feels it is in the participant's best interest, but the reasons for doing so should be recorded. In these cases the participants remain within the study for the purposes of follow-up and data analysis. All participants are free to withdraw at any time from the protocol treatment without giving reasons and without prejudicing further treatment.

8.3 CONFIDENTIALITY

The Chief Investigator will preserve the confidentiality of participants taking part in the study and is registered under the Data Protection Act.

8.4 INDEMNITY

Imperial College London holds negligent harm and non-negligent harm insurance policies which apply to this study/ Imperial College Healthcare NHS Trust holds standard NHS Hospital Indemnity and insurance cover with NHS Litigation Authority for NHS Trusts in England, which apply to this study (delete as applicable)

8.5 SPONSOR

Imperial College London/Imperial College Healthcare NHS Trust (delete as applicable) will act as the main Sponsor for this study. Delegated responsibilities will be assigned to the NHS trusts taking part in this study.

8.6 FUNDING

We have applied for funding from the wellbeing of women charity.

8.7 AUDITS

The study may be subject to inspection and audit by Imperial College London under their remit as sponsor and other regulatory bodies to ensure adherence to GCP and the NHS Research Governance Framework for Health and Social Care (2nd edition).

9. STUDY MANAGEMENT

The day-to-day management of the study will be co-ordinated through [name], clinical research fellow.

10. PUBLICATION POLICY

The data obtained from this study will be anonymised and analysed. The anonymised data will be published in peer-reviewed journals and presented in relevant conferences and at patient/public engagement events.
